4.0 Methods

4.1 Study Sites

The study will be conducted in two large academic-affiliated health networks (Wake Forest Baptist Health and UNC) that have over 200 community-based primary care clinics with approximately 900 PCPs and a catchment area covering all of North Carolina and extending to four neighboring states, including portions of rural Appalachia. In 2018 both networks saw 165,601 “ever smokers” who were potentially eligible for LCS based on age. Both health networks have the same EHR (EpicTM, Verona, WI) that is shared by all of their clinics.

LCS programs and usual care. Both networks have well-established LCS programs. Patients, who may self-refer to the LCS program, meet with a provider who confirms screening eligibility, conducts a shared decision making visit in accordance with CMS guidelines,⁸ and orders the screening CT. Afterwards, the LCS clinic communicates results to the patient and arranges any needed follow-up testing. Primary care providers may also order screening CTs directly, in which case they must conduct the shared decision making visit, communicate results, and order any needed follow-up testing. Both networks broadly advertise their LCS programs to patients via web campaigns, posters, and mailings. Despite these efforts, only 2% of those potentially eligible in 2018 (3,215 of 165,601) were screened.

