5.2 Secondary Outcomes

- 5.2.1 LCS screening decisions: LCS screening decisions will be captured by the mPATH-Lung program in the mPATH-Lung group only. (Time frame = post-intervention)
- 5.2.2 LCS clinic visits scheduled: The proportion of patients in each arm who have scheduled a LCS clinic visit will be captured by querying the EHR at each site.
- 5.2.3 LCS clinic visits completed: The proportion of patients in each arm who have completed a LCS clinic visit will be captured by querying the EHR at each site.
- 5.2.4 LCS scans ordered: The proportion of patients in each arm for whom a LCS scan was ordered will be captured by querying the EHR at each site.
- 5.2.5 LCS Clinic referral requested through mPATH
- 5.2.6 Lung RADS Results: The results of all chest CTs will be captured by querying the EHR at each site.
- 5.2.7 LCS false positives: A false positive scan will be defined as a Lung-RADS 3 or 4 result with a negative completed work-up for lung cancer or no diagnosis of lung cancer within 12 months of the scan.
- 5.2.8 Invasive procedures following LCS scan: We will query the EHR at each site to determine the number and proportion of patients in each arm who undergo an invasive procedure to investigate an abnormal LCS scan.
- 5.2.9 Complications following LCS: We will query the EHR at each site and conduct a blinded chart review to determine the number and proportion of patients in each arm who experience a complication from an invasive procedure done to investigate an abnormal LCS scan.
- 5.2.10 Number of diagnosed lung cancers (detected by screening or other) within 16 months of randomization
- 5.2.11 Whether diagnosed lung cancers were detected incidentally or related to screening
- 5.2.12 Stage of lung cancers diagnosed
- 5.2.13 Overscreening: We will determine the proportion of patients with screen diagnosed lung cancer in the mPATH-Lung and control groups who are deemed too ill for potentially curative surgery by blinded chart review.
- 5.2.14 Reach of digital outreach strategy: Reach of the digital outreach strategy is defined as the proportion of patients who complete the website study eligibility questions. The denominator includes all patients who were sent an invitation, regardless of full program completion and whether or not they were subsequently determined to be eligible for LCS.

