6.0 Analytic Plan

6.1 Primary Analysis

The primary analysis will be carried out based on "intent to treat." All patients will be included in their randomized arm whether or not they actually finish the program. The primary objective of effectiveness will be assessed using a logistic regression model with completion of LCS (Y/N) within 16 weeks of enrollment as the outcome, treatment arm as the primary independent variable, and health system as a covariate per the design.

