6.2 Secondary Analyses

In secondary analyses of effectiveness, we will assess the effects of age, sex, race and ethnicity, insurance status, and rurality on screening rates using logistic regression models. Additionally, we will conduct separate subgroup analyses for these covariates to obtain estimates and 95% confidence intervals of the intervention effect in these subgroups.

This same strategy described for analysis of completion of LCS to assess the effectiveness of the mPATH-Lung program will be used to assess the impact of the mPATH-Lung program on screening intent, scheduled and completed LCS clinic visits, test ordering, and screening-related harms (including overscreening). For LCS results, we will provide estimates with confidence intervals for the proportion of patients who have Lung-RADS 1 (normal), Lung-RADS 2 (small/stable nodule), Lung-RADS 3 (nodule with 6-month follow-up recommended), and Lung-RADS 4 (concerning nodule needing short-term follow-up or biopsy) results. Ordinal logistic or linear regression will be used to assess the effect of mPATH-Lung on patient knowledge of LCS, depending on the distribution of the outcome. We will also examine knowledge levels in those with a strong preference for or against screening.

We will use descriptive statistics to characterize participants' screening decisions, ratings on the values clarification exercise, most important attributes, and screening behavior. We will use multinomial logistic regression to examine the relationships between the most important attribute and screening decision, where the outcome is coded on three levels (want screening, unsure, do not want screening). We will include the following covariates in the model: age, sex, pack-years of smoking, knowledge score, and 5-year life expectancy (to capture comorbidity) using a previously validated model.^{66,67}

We will use descriptive statistics to characterize *Reach* and *Acceptability* by patient sociodemographic characteristics and invitation modality, and the *Appropriateness* by provider and practice characteristics. Similar to our strategy for analyzing our primary outcome, we will use logistic regression to examine the effect of patient characteristics on the *Reach* measures.

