6.4 Sample Size and Power

In 2015 (the year Medicare approved payment for LCS), only 3.9% of eligible Americans were screened.⁹ Given that national screening rates are expected to increase, we will conservatively assume the screening rate in the control group will be 10%. A total sample size of 1320 patients (approximately 660 in each group) will provide 90% power for detecting a 6% absolute difference in screening rates at the 5% two-sided level of significance and approximately 80% power for detecting a 5% absolute difference in screening. Because our primary outcome measure is determined by electronic health record review and not surveys, there will be no loss to follow-up.

We anticipate sending approximately 26,000 electronic invitations to identify and accrue 1320 eligible patients. This sample size of 26,000 invitations will allow us to estimate the *Reach* of the electronic invitations to within $\pm 0.6\%$. Our sample size of 660 patients in the mPATH-Lung arm will allow us to estimate the *Reach* of mPATH-Lung (the proportion of those who complete it) to within $\pm 3.8\%$. Our sample size of 660 patients in the mPATH-Lung arm will allow us to estimate the mean *Acceptability* score to within ± 0.076 SD. Due to the highly pragmatic nature of this study, our planned sample size will stay 660, but we may over-enroll because it takes time to change the mPATH codebase once accrual targets are reached. While we are changing the codebase, participants who received invitations may continue to visit the mPATH web app and be randomized. Therefore, we acknowledge we may over-enroll by a few participants.

Following completion of primary data collection, we will invite all primary care providers who had at least one patient randomized to mPATH-Lung to respond to a brief emailed survey. We expect 466 primary care providers will have at least 1 patient in the mPATH-Lung arm (based on the binomial probability assuming 660 patients in the mPATH-Lung arm and an equal probability of seeing one of 890 health system providers). Based on our prior studies surveying providers (with response rates of 40% - 60%),^{38,70} we conservatively estimate 30% will respond which will yield approximately 140 completed surveys. Our sample size of 140 providers will allow us to estimate the mean *Appropriateness* score to within ± 0.17 SD.

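### The invitation-Reach regressions make no allowance for clinic, so standard errors for characteristics that differ mainly between clinics will be too small if response is correlated within clinic.

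*Combined protocol and SAP*

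**What the plan says.** Section 5.2.14 defines Reach of the outreach strategy as the proportion who complete the website eligibility questions: "The denominator includes all patients who were sent an invitation". Section 6.4 sets the size: "We anticipate sending approximately 26,000 electronic invitations to identify and accrue 1320 eligible patients". It gives a precision of ±0.6% for this proportion. Section 4.1 describes networks with "over 200 community-based primary care clinics with approximately 900 PCPs", and section 3.1 requires each invitee to have a primary care visit scheduled.

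For the models, section 6.2 says: "Similar to our strategy for analyzing our primary outcome", "we will use logistic regression to examine the effect of patient characteristics on the" Reach measures. The strategy referred to is in section 6.1: a logistic model with treatment arm and "health system as a covariate per the design". The documents mention no clinic or provider effect, no GEE, no cluster-robust variance and no ICC.

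The characteristics to be examined for Reach are not itemised. Reach is to be described "by patient sociodemographic characteristics and invitation modality". The explicit list that includes insurance and rurality belongs to a different outcome: "we will assess the effects of age, sex, race and ethnicity, insurance status, and rurality on screening rates using logistic regression models".

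**The concern.** Borrowing the primary-analysis model is safe for the primary question and less so for this one. Arm is assigned patient by patient, so it is essentially unrelated to clinic, and within-clinic correlation does little to the standard error of the arm effect. Patient characteristics are observed. Some follow clinic geography, and invitees attending the same clinic may also resemble each other in how readily they respond. When both are true, the effective sample for that characteristic is smaller than 26,000 and the ordinary model does not know it.

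Reach is a named secondary outcome, and section 2.2 wants it to inform whether the programme can be scaled to varied primary care settings. These regressions are where the trial would report which patients the outreach tends to miss. With this many records, modest clinic-to-clinic differences can look like firm patient-level associations.

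**Working it through.** **Inputs from the documents.** N = 26,000 invitations (6.4). Clinics: over 200 (4.1). mPATH-Lung arm: 660 (6.4). Pilot response: 35% (6.5).

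**Inputs assumed, because the documents do not give them.** Within-clinic ICC of response (ICC_y) from 0.001 to 0.02. Within-clinic ICC of the covariate (ICC_x) from 0 (unrelated to clinic) to 1 (constant within clinic). Equal clinic sizes unless stated.

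**Step 1: the plan's own figure.** Under independence the half-width is 1.96 × √(p(1−p)/N).
- p = 0.5: 1.96 × √(0.25/26,000) = 0.608%
- p = 0.35: 1.96 × √(0.2275/26,000) = 0.580%

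Both round to the stated ±0.6%. The figure is therefore a simple-random-sample calculation, consistent with reading the regressions as assuming independence too.

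**Step 2: cluster size.** m = 26,000/200 = 130 per clinic. This is an upper bound on the average, because there are more than 200 clinics.

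**Step 3: design effect.** DE = 1 + (m − 1) × ICC_y × ICC_x = 1 + 129 × ICC_y × ICC_x. The true standard error divided by the model-based one is √DE. The actual two-sided rejection rate at nominal 5% is 2 × [1 − Φ(1.96/√DE)].

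| ICC_x | ICC_y | DE | SE ratio | Rejection rate |
|---|---|---|---|---|
| 1 | 0.001 | 1.13 | 1.06 | 6.5% |
| 1 | 0.005 | 1.65 | 1.28 | 12.6% |
| 1 | 0.01 | 2.29 | 1.51 | 19.5% |
| 1 | 0.02 | 3.58 | 1.89 | 30.0% |
| 0.5 | 0.005 | 1.32 | 1.15 | 8.8% |
| 0.5 | 0.01 | 1.65 | 1.28 | 12.6% |
| 0.5 | 0.02 | 2.29 | 1.51 | 19.5% |
| 0.2 | 0.005 | 1.13 | 1.06 | 6.5% |
| 0.2 | 0.01 | 1.26 | 1.12 | 8.1% |
| 0.2 | 0.02 | 1.52 | 1.23 | 11.1% |
| 0 | any | 1.00 | 1.00 | 5.0% |

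**Step 4: unequal clinic sizes and the remedy.** A simulation used 200 clinics, 26,000 invitees, an assumed 17.5% response, clinic sizes with a coefficient of variation of 0.8, ICC_y 0.005 to 0.02, ICC_x 0.2 to 0.5 and 600 runs per setting. The ordinary model rejected a true null in about 9% to 23% of runs. Clinic-clustered errors brought this to 4% to 6%. The Monte Carlo standard error is 1 to 2 percentage points, for example √(0.23 × 0.77/600) = 1.7%, so the low end is only loosely determined.

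**Step 5: the other Reach measure.** For programme completion, 660/200 = 3.3 patients per clinic. DE for a clinic-constant covariate is 1 + 2.3 × 0.01 = 1.02 at ICC 0.01 and 1 + 2.3 × 0.05 = 1.12 at ICC 0.05. That is negligible to small.

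**Step 6: overall Reach.** Multiplying ±0.608% by √DE gives ±0.78% at ICC 0.005 (×1.28) and ±0.92% at ICC 0.01 (×1.51).

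**The case against.** The strongest case against has four parts.

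- **No ICC is given.** Invitations go directly to patients by portal message or text, and no clinic role in delivery is described. The correlation left after adjusting for covariates and health system could be very small. This stands as a limit on size: at ICC 0.001 the understatement is at most about 6%.
- **Clinics are not sampled.** Patients are selected individually from each network's records. If the target is Reach in these two networks alone, the clinics are a fixed population, and a rural gap that operates through clinics is a real gap there. This largely stands for the overall Reach proportion. It carries less weight for the regressions, because section 2.2 looks beyond these clinics to scaling in varied settings, which makes clinic-to-clinic variation part of the uncertainty.
- **Rurality and insurance are listed for screening rates, not Reach.** This stands. Their use for Reach is a reasonable inference only. Insurance, if it varies mostly within clinics, would be affected much less than rurality.
- **No significance threshold is set for the Reach models.** This also stands. The rejection rates above are best read as lost coverage: 12.6% means that a nominal 95% interval covers 87.4% of the time.

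A reader might infer that the standard errors are known to be understated by 1.3- to 1.9-fold, or that reported disparities by rurality or insurance would be false. The documents support neither. That range needs a covariate constant within clinic and an ICC of 0.005 to 0.02, and the plan sets no rule by which a disparity would be declared.

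**Conclusion.** The point holds conditionally. The plan specifies an independence model for observational associations in data grouped by clinic, and any positive within-clinic correlation of response makes intervals too narrow for characteristics that cluster by clinic. For partly patterned characteristics the rejection rate at nominal 5% is roughly 6.5% to 20% with equal clinic sizes, and somewhat higher if sizes are unequal. These figures rest on assumed ICCs and on 130 invitees per clinic, which is an upper bound on the average. A characteristic unrelated to clinic is unaffected.

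The scope is limited to the invitation-Reach models. It would be wrong to extend the point to the primary comparison: randomisation is at patient level, stratified by network. It is a secondary matter for the trial, but it is worth correcting because the error runs in one direction and bears on a stated objective.

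**What to change.** In section 6.2, state that the invitation-Reach models will use cluster-robust standard errors (sandwich or GEE) by clinic of the scheduled visit, or a clinic random intercept. With about 200 clinics there are enough clusters for this to work well, and if the ICC is near zero the intervals will hardly change.

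Also specify that a de-identified clinic code is retained for every invitee, responders and non-responders alike. The scheduled-visit criterion suggests the clinic can be obtained, but the documents do not say that the record query returns it, and section 8.0 does not mention it among the fields kept. It would help to list the characteristics to be examined for Reach at the same time.

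The cost is a sentence or two of plan text, one model option, one extra data field to be kept under the existing confidentiality arrangements, and wider intervals for some characteristics. A clinic-clustered interval for overall Reach beside the crude one is optional.

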6.3 Qualitative Analyses

Telephone interviews will be recorded and transcribed verbatim. Transcripts will be reviewed against the original audio for quality control before being imported into Atlas.ti software⁶⁸ for coding and data management. Interview transcripts will be paired with individual demographic data and post-program survey responses. We will develop the initial codebook using the interview guide and survey items as a structure. We will then use an inductive approach to modify the initial codebook as new themes emerge. All emergent themes will be discussed amongst the team during the coding process. New codes and definitions will be agreed upon by group consensus. All transcripts

will be dual coded and differences will be discussed and resolved by consensus. Segments of text will be abstracted by code or code combinations and iteratively reviewed/summarized as a team. Themes will be determined by the prevalence and salience in the data.⁶⁹ Qualitative outcomes for providers will be compared between the two health networks.

6.4 Sample Size and Power

In 2015 (the year Medicare approved payment for LCS), only 3.9% of eligible Americans were screened.⁹ Given that national screening rates are expected to increase, we will conservatively assume the screening rate in the control group will be 10%. A total sample size of 1320 patients (approximately 660 in each group) will provide 90% power for detecting a 6% absolute difference in screening rates at the 5% two-sided level of significance and approximately 80% power for detecting a 5% absolute difference in screening. Because our primary outcome measure is determined by electronic health record review and not surveys, there will be no loss to follow-up.

We anticipate sending approximately 26,000 electronic invitations to identify and accrue 1320 eligible patients. This sample size of 26,000 invitations will allow us to estimate the *Reach* of the electronic invitations to within $\pm 0.6\%$. Our sample size of 660 patients in the mPATH-Lung arm will allow us to estimate the *Reach* of mPATH-Lung (the proportion of those who complete it) to within $\pm 3.8\%$. Our sample size of 660 patients in the mPATH-Lung arm will allow us to estimate the mean *Acceptability* score to within ± 0.076 SD. Due to the highly pragmatic nature of this study, our planned sample size will stay 660, but we may over-enroll because it takes time to change the mPATH codebase once accrual targets are reached. While we are changing the codebase, participants who received invitations may continue to visit the mPATH web app and be randomized. Therefore, we acknowledge we may over-enroll by a few participants.

Following completion of primary data collection, we will invite all primary care providers who had at least one patient randomized to mPATH-Lung to respond to a brief emailed survey. We expect 466 primary care providers will have at least 1 patient in the mPATH-Lung arm (based on the binomial probability assuming 660 patients in the mPATH-Lung arm and an equal probability of seeing one of 890 health system providers). Based on our prior studies surveying providers (with response rates of 40% - 60%),^{38,70} we conservatively estimate 30% will respond which will yield approximately 140 completed surveys. Our sample size of 140 providers will allow us to estimate the mean *Appropriateness* score to within ± 0.17 SD.

6.5 Accrual Rate

In our prior pilot study limited to patients with active portal accounts in a single health system, it required 10 weeks to identify 1000 potentially eligible patients, of whom 35% (349) completed our study program, and 10% (99) were found to be eligible for LCS, yielding 10 patients per week.¹ For this pragmatic trial, we will accrue patients from two health networks and also include patients with cellphone numbers or email addresses, significantly expanding the pool of eligible participants. Patients without portal accounts may be less likely to respond, so we conservatively estimate that we will accrue patients at half the rate (5%) of our pilot study. Therefore, we will send invitations to 260 patients per week (130 at Wake Forest and 130 at UNC) to accrue 13 patients per week, completing accrual over 2 years. We will oversample for non-white patients. We will monitor accrual rates and increase the number of invitations sent as needed.

6.6 Study Timeline

Study Task	Year 1				Year 2				Year 3				Year 4				Year 5			
	Q 1	Q 2	Q 3	Q 4	Q 1	Q 2	Q 3	Q 4	Q 1	Q 2	Q 3	Q 4	Q 1	Q 2	Q 3	Q 4	Q 1	Q 2	Q 3	Q 4
Values clarification exercise development and pre-testing	X	X																		
mPATH-Lung program revisions and testing	X	X	X																	
Electronic health record integration and testing				X	X															
Patient/provider survey development and pre-testing				X	X															
Pragmatic trial enrollment (Aim 1)					X	X	X	X	X	X	X	X								
Lung cancer screening outcomes data collection (Aim 1)						X	X	X	X	X	X	X	X	X	X					
Surveillance tracking of false positives and harms (Aim 1)						X	X	X	X	X	X	X	X	X	X	X	X	X	X	
Data cleaning					X	X	X	X	X	X	X	X	X	X	X	X	X	X	X	
Patient interviews about values/drivers of screening decisions (Aim 2)						X	X	X	X	X	X	X	X	X						
PCP surveys and interviews about mPATH-Lung appropriateness/implementation (Aim 3)																X	X	X		
Data analysis																	X	X	X	X
Results dissemination																	X	X	X	X

7.0 Data Management and Security

All mPATH-Lung interaction data including the embedded self-surveys will be stored on a central Wake Forest data server using industry standard encryption (e.g., AES-256 bit) to protect personal health information. The mPATH-Lung and EHR data will be monitored closely and reviewed at study staff meetings every 2 weeks during enrollment. Quality control information (surveys due/completed, data entered, missing data, out of range data, inconsistent EHR data, etc.) will also be summarized and reviewed, along with accrual rates.

8.0 Confidentiality and Privacy

Confidentiality will be protected by collecting only information needed to assess study outcomes, minimizing to the fullest extent possible the collection of any information that could directly identify subjects, and maintaining all study information in a secure manner. To help ensure subject privacy and confidentiality, only a unique study identifier will appear on data collection forms and in study datasets. Any collected patient identifying information corresponding to the unique study identifier will be maintained in a linkage file, stored separately from the data. The linkage file will be kept secure, with access limited to designated study personnel. An honest broker will mediate the electronic health record data queries to limit the exposure of patient identifying information.

Because some study outcomes will require a manual chart review (for example, determination of “overscreening”), the honest broker will create a linkage file containing electronic health record numbers that only the study data analyst can access. All personal identifiers (other than dates of service and patient zip code) will be removed from the study datasets and only the study ID included. One year after publication of the main study findings, the linkage file will be destroyed (electronically deleted or shredded in the case of paper forms). Data access will be limited to study staff. Data and records will be kept locked and secured, with any computer data password protected. No reference to any individual participant will appear in reports, presentations, or publications that may arise from the study.

